- d. Day 1 of Cycle 1 is defined as the day of first administration of brentuximab vedotin. Screening evaluations performed within 14 days prior to start of protocol therapy may serve as Day 1 baseline evaluations, **except** for pregnancy test which must be performed within 24 hours prior to Day 1 of protocol therapy.
- e. Activities (**except** imaging and response assessment) and safety assessment review to be performed within 72 hours prior to initiation of the new cycle.
- f. The 30 days post-last dose assessments to occur 30 (-2/+7) days post-last dose or, if > 30 days elapsed since last dose, within 7 days after decision to end treatment. Expedited reporting will occur during this period (see [Section 7.8](#)).
- g. The 100 days post-last dose assessments to occur 100 (-7/+28) days post-last dose or at initiation of a new anticancer therapy. Expedited reporting will occur during this period (see [Section 7.8](#)). Safety follow-up may be extended until resolution/ stabilization of reportable AEs.
- h. For participants who ended protocol therapy and have yet to progress/relapse, Active follow-up visit to occur at 3 months (± 14 days), 6 months (± 14 days), 12 months (± 28 days) and 18 months (± 28 days) from start of treatment until progression or initiation of new anticancer therapy.
- i. The Safety assessments/activities may be joint with Active Follow-up assessments/activities if the windows for the two visits overlap.
- j. The 3 month Active Follow-up activities to occur if the participant ended protocol therapy prior to the Cycle 4 Day 15 scan.
- k. The 6 month Active Follow-up activities to occur if the participant ended protocol therapy prior to Cycle 8.
- l. Long-term follow-up for those for all participants who have progressed/relapsed OR completed Active Response Follow-Up. Assessment to occur biannually or as requested by the Study PI via medical record review, review of social security registry/ public records, and/or telephone call.
- m. Informed consent process to be fully documented (see [Section 16.4](#)). Informed consent must occur prior to any research only (non-SOC) screening procedures.
- n. Eligibility criteria are detailed in [Section 3.0](#).
- o. Registration in a COH clinical trial management system (CTMS).
- p. Medical history to include a review of treatment history, any ongoing medical conditions and medical history pertaining to eligibility on study and involvement during study.

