11.1.2 Clinical Endpoints

Evaluable patients are defined as eligible participants who received at least one dose of the protocol treatment. Eligible participants who did not receive any protocol treatment will be considered in-evaluable, replaced, and excluded from all analyses.

Endpoint	Patients	Definition
Progression-Free Survival (PFS)*	Evaluable patients	Defined as the time from the first dose of study treatment to the first observation of disease relapse/progression or death from any cause, whichever occurs first. For patients who are alive and have not had disease relapse/progression at the last follow-up, it is censored at the time of last follow-up. If a patient receives non-protocol anti-HL treatment prior to disease relapse/progression, the patient will be censored at the time of non-protocol anti-HL treatment.

Endpoint	Patients	Definition
Overall Survival (OS)	Evaluable patients	Defined as the time from the first dose of study treatment to death from any cause. For patients alive at the last follow-up, it is censored at the time of last follow-up.
Cumulative Incidence of Non-Relapse Mortality (NRM)*	Evaluable patients	Defined as the time from the first dose of study treatment to non-disease related death. Disease relapse or progression is considered a competing risk. For surviving patients without disease relapse/progression at the last follow-up, it is censored at the time of last follow-up. If a patient receives non-protocol anti-HL treatment prior to disease relapse/progression, the patient will be censored at the time of non-protocol anti-HL treatment.
Cumulative Incidence of Relapse/Progression*	Evaluable patients	Defined as the time from the first dose of study treatment to disease relapse/progression. Death without relapse/progression is considered a competing risk. For surviving patients without relapse/progression at the last follow-up, it is censored at the time of last follow-up. If a patient receives non-protocol anti-HL treatment prior to disease relapse/progression, the patient will be censored at the time of non-protocol anti-HL treatment.
Overall response rate (ORR)	Evaluable patients with measurable disease post-ASCT	Proportion of patients achieving CR or PR [53]

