12.0 STATISTICAL CONSIDERATIONS

12.1 Study Design

This is a single-arm, open-label Phase 2 study of nivolumab plus BV consolidation following ASCT in patients with relapsed/ refractory HL who have undergone ASCT. Participants will receive protocol treatment consisting of 21-day cycles, for up to 8 cycles. The primary endpoint is 18-month progression-free survival. Secondary endpoints include overall survival, cumulative incidence of relapse/progression, cumulative incidence of non-relapse mortality, overall response rate, and toxicity. The target sample size is 59 eligible participants who received at least one dose of the protocol treatment. Eligible participants who did not receive any protocol treatment will be considered in-evaluable and replaced. The total study accrual may be increased slightly beyond 59 patients in order to achieve 59 evaluable participants with at least one dose. To account for up to 10% inevaluable enrollments, the maximum study accrual is set to be 65 participants. The projected study accrual duration is 24 months at the estimated accrual rate of 2-3 patients per month. With a planned follow-up until 18 months from the first dose of study treatment for the last accrued patient, the projected total study duration for accrual and follow-up is approximately 42 months.

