12.3 Statistical Analysis Plan

12.3.1 Power Estimation

The primary endpoint is 18-month PFS, as defined in [Section 11.0](#). Eligible participants who received at least one dose of the protocol treatment will be evaluable for the primary endpoint; eligible participants who did not receive any protocol treatment will be considered in-evaluable and excluded from all analyses.

Based on the AETHERA trial, the 18-month PFS rate in patients with relapsed/refractory HL who undergo ASCT followed by BV consolidation is approximately 65% (from the independent assessment data) [32]. We hypothesize that adding nivolumab to BV consolidation after ASCT will improve the 18-month PFS rate to 80%. A sample size of 59 evaluable patients will provide approximately 81% power for detecting the

increase in 18-month PFS from the baseline of 65% to 80% in this study at 1-sided type I error of 0.05. The power estimation is based on the exact binomial test. Operationally, the study treatment will be considered promising if at least 45 of the 59 evaluable participants are alive and progression-free at 18 months after the first dose of study treatment. The probability of observing at least 45 surviving and progression-free participants out of a total 59 participants, assuming different PFS rates, is shown in [Table 12.3.1](#).

Table 12.3.1 The probability of declaring the trial a success assuming different PFS rates

	True 18-month PFS rate			
	65%	70%	75%	80%
The probability of observing at least 45 participants (out of 59 total) being alive and progression-free at 18-month	0.044	0.18	0.48	0.81

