12.3.2 Analysis Plans

Patient demographics and baseline disease characteristics, including age, gender, medical history, and prior therapy, will be summarized using descriptive statistics. For continuous variables, descriptive statistics such as number, mean, standard deviation, standard error, median (range) etc. will be provided. For categorical variables, patient counts and percentages will be provided.

For all analyses, only eligible participants who received at least one dose of protocol treatment will be considered evaluable and included in the analyses. Eligible participants who did not receive any protocol treatment will be considered in-evaluable and excluded from all analyses.

PFS will be estimated using the product-limit method of Kaplan and Meier along with the Greenwood estimator of standard error. When there is no censoring in PFS prior to 18 months after the first dose of study treatment, the observed 18-month PFS will be compared to the baseline of 65% by one-sided exact test of binomial proportion. In case of censoring in PFS prior to 18 months after the first dose of study treatment (which are expected to be rare), the Kaplan-Meier estimate for 18-month PFS along with the Greenwood standard error estimator will be used for the testing of null hypothesis at 65%.

OS will be estimated using the product-limit method of Kaplan and Meier along with the Greenwood estimator of standard error. Cumulative incidence of relapse/progression and cumulative incidence of non-relapse mortality, as well as their confidence intervals will be estimated using competing risk methodology, treating the other event as a competing risk. Overall response rate will be estimated by the proportion of patients achieving either CR or PR among participants with measurable disease after ASCT, along with the exact binomial confidence interval.

Observed toxicities will be summarized by type (organ affected or laboratory determination such as absolute neutrophil count), severity (by NCI CTCAE v4.0 and nadir or maximum values for lab measures), date of onset, duration, reversibility, and attribution.

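### The fallback test in 12.3.2 names no scale; untransformed, with censoring only after the last event, it rejects at 44 of 59, one below the 45 that 12.3.1 requires

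*Combined protocol and SAP*

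**What the plan says.** - **Success rule (12.3.1).** With 59 evaluable patients, a 65% null and one-sided alpha 0.05, "the study treatment will be considered promising if at least 45 of the 59 evaluable participants are alive and progression-free at 18 months".
- **Definition and censoring (11.1.2).** PFS is "the time from the first dose of study treatment to the first observation of disease relapse/progression or death from any cause, whichever occurs first". The rule for the rest: "For patients who are alive and have not had disease relapse/progression at the last follow-up, it is censored at the time of last follow-up". The section does not say whether last follow-up means the last scan or the last contact. Non-protocol anti-HL treatment before progression also censors.
- **Test (12.3.2).** The exact one-sided binomial test applies when there is no censoring before 18 months. The condition for the alternative is "In case of censoring in PFS prior to 18 months after the first dose of study treatment (which are expected to be rare"). What the section then prescribes is this: "the Kaplan-Meier estimate for 18-month PFS along with the Greenwood standard error estimator will be used for the testing of null hypothesis at 65" percent. No transformation is named.
- **Visit window (10.0, footnote h).** Active follow-up visits include "12 months (± 28 days) and 18 months (± 28 days) from start of treatment".
- **Later contact.** Section 5.7 collects disease and vital status in long-term follow-up for up to five years from start of treatment. Footnote l of 10.0 gives the frequency: "Assessment to occur biannually or as requested by the Study PI via medical record review". The study duration in 12.1 is built on this: "With a planned follow-up until 18 months from the first dose of study treatment for the last accrued patient".

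**The concern.** The plan has two primary tests, and a single censored patient decides which one is used. They need not have the same bar. If the fallback accepts a result that the exact test and the count of 45 reject, the type I error stated in 12.3.1 no longer describes the procedure. At 44 of 59 the sections would then disagree, and nothing says which prevails.

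Full compliance with the calendar can produce the switch. Eighteen months is about day 548, so an in-window scan may fall as early as about day 520. If that scan is clean and nothing later is on file at data cut-off, the patient is censored before 18 months. The trial has no control arm and its conclusion rests on this one test.

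**Working it through.** **Inputs.** n = 59, null 0.65, alternative 0.80, one-sided alpha 0.05 and cut-off 45, all from 12.3.1. Critical z = 1.645.

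**1. The plan's own figures.** P(X ≥ 45 | 59, p) = 0.0436, 0.1825, 0.4801 and 0.8124 at p = 0.65, 0.70, 0.75 and 0.80. These match the table in 12.3.1.

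**2. The exact test one patient lower.** P(X ≥ 44 | 59, 0.65) = 0.0775, so 44 is not a rejection. P(X ≥ 44 | 59, 0.80) = 0.8836.

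**3. The fallback, untransformed.** Take 15 events and 44 patients without an event, one of them censored at day 530, after the last event. No event follows the censoring, so the Kaplan-Meier estimate is S = 44/59 = 0.7458. The Greenwood standard error reduces to √(S(1−S)/59) = √(0.7458 × 0.2542/59) = 0.0567. Then z = (0.7458 − 0.65)/0.0567 = 1.69.

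**4. The fallback, log-log.** z = [ln(−ln 0.65) − ln(−ln S)] / [SE/(S·|ln S|)]. At 44 this is 0.384/0.259 = 1.48; at 45 it is 1.73.

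| Event-free of 59 | Exact p | Untransformed z (p) | Log-log z (p) |
|---|---|---|---|
| 43 | 0.128 | 1.36 (0.087) | 1.23 (0.109) |
| 44 | 0.077 | 1.69 (0.046) | 1.48 (0.069) |
| 45 | 0.044 | 2.04 (0.021) | 1.73 (0.042) |

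On other scales at 44, the log scale rejects (p = 0.035). Logit (0.063), arcsine (0.054) and the null-variance form (0.062) do not.

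**5. Dependence on when censoring occurs.** Keep 44 event-free patients and the untransformed scale. If the last event falls at day 535, after censoring at day 520, z is 1.680 with one patient censored (rejects), 1.637 with five and 1.348 with twenty (neither rejects). One patient censored mid-course gives z = 1.63 (does not reject). So 44 is the cut-off only when censoring comes at or near the end of the event times.

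**6. Effect on the whole procedure.** With late censoring, the tests differ only at exactly 44. P(X = 44 | 0.65) = 0.0775 − 0.0436 = 0.0339. Let s be the share of trials ending at 44 in which the switch occurs. Overall type I error is 0.0436 + 0.0339 × s. The documents do not give s, so the full range is:

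| s (assumed) | Type I error |
|---|---|
| 0 | 0.044 |
| 0.10 | 0.047 |
| 0.19 | 0.050 |
| 0.50 | 0.061 |
| 1 | 0.077 |

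The 0.05 limit is reached at s = (0.05 − 0.0436)/0.0339 = 0.19.

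**The case against.** The trigger is narrower than the visit window alone suggests. An early clean scan matters only if nothing later is on file. The synopsis sets a minimum participation of 18 months from start of treatment. Section 5.7 continues to collect disease status, and footnote l allows contact at the Study PI's request as well as twice a year. No section fixes the data cut-off at the last scan. One status check before lock would remove most such cases, and 12.3.2 itself expects them to be rare. If just one patient lacked later contact and 10% of scans were early (both assumed), then s is about 44/59 × 0.10 = 0.075 and type I error 0.0436 + 0.0339 × 0.075 = 0.046, within the stated 0.05. All of this stands. It limits how often the switch occurs, but leaves open which scale applies when it does.

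It can also be said that a statistician would choose log-log anyway. The plan does not say so, and the literal reading is the untransformed one.

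A reader might infer that the window routinely inflates the error rate, or that the fallback always accepts 44. The documents support neither: the first needs a switching frequency they do not give, and the second fails on several scales and under earlier or multiple censoring. A reader might also infer that scans up to 28 days late bias the result. But 11.1.2 already dates PFS to first observation, and the documents do not say how the 65% benchmark was dated, so neither a direction nor a size can be shown.

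**Conclusion.** The concern holds in a conditional form. Section 12.3.2 leaves open a choice that can decide the trial at 44 of 59. Untransformed, with censoring only after the last event, the fallback rejects there (p = 0.046), while the exact test (p = 0.077) and the count of 45 do not. If that fallback always applied under such censoring, type I error would be 0.077 and power 0.88. Across all possible switching frequencies the type I error lies between 0.044 and 0.077, and it exceeds 0.05 only when s is above about 0.19.

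The early side of the ±28-day window is one route to the switch. Censoring at non-protocol therapy is another, although mid-course censoring can move 44 back to non-rejection. No claim is made about late in-window scans. The gap should be closed before analysis because it bears on the primary test and costs little to close.

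**What to change.** 1. In 12.3.2, specify the log-log scale for the Kaplan-Meier/Greenwood test. This keeps the bar at 45 of 59 when the only censoring is just before 18 months. State that the fallback replaces the 45-of-59 count when there is censoring before 18 months, so that 12.3.1 and 12.3.2 cannot conflict.
2. Before data lock, use the contact already allowed by 5.7 and footnote l to obtain disease and vital status dated on or after 18 months for every patient who is alive and progression-free. List any patient without it.

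**Cost.** A few sentences and one round of record review or telephone contact, with no extra scans. Power is the stated 0.81, not the 0.88 of the lower bar. Status from record review is weaker evidence of no progression than a scan, so its use should be reported.

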11.0 ENDPOINT EVALUATION CRITERIA/MEASUREMENT OF EFFECT

11.1 Response, Clinical Endpoints and Toxicity

11.1.1 Response/Progression

HL response/progression will be evaluated using 2014 Lugano Classification (see [Table 11.1](#)) [53, 54]. Participants who meet the definition of progressive disease per Lugano Classification should be evaluated using the LYRIC criteria (see [Appendix H](#)).

PET-CT or diagnostic quality CT of the neck, chest, abdomen, and pelvis (N/C/A/P) with IV contrast will be performed at baseline and the pre-specified time points in the study calendar. PET and CT may be co-acquired or acquired separately. Additional necessary restaging studies including dedicated CT scans, MRI, or bone marrow biopsies, are permitted at the investigator's discretion. Although diagnostic quality CT is acceptable, PET-CT is the preferred disease assessment method throughout the study, particularly for patients not in CR. Since 18-month PFS is the primary endpoint, every effort should be made to perform PET-CT at the "18-month from start of treatment" time point (particularly if the patient never achieved CR after ASCT), but if not possible, diagnostic quality CT will be acceptable. PET-CT and CT results will be read by a radiologist at each study site and investigator response based on radiology reading will be performed.

For patients with progression of disease on imaging, it is strongly recommended that a confirmatory biopsy be obtained whenever possible. Note that an FDG-negative PET scan will only be considered complete remission in patients whose tumor was FDG-avid at baseline.

A disc copy of the study-required images, including post-salvage/pre-ASCT PET scan should be sent to the Study PI upon request. Per institutional practices, the images should be de-identified (coded) and the disc should be labeled with Subject ID, COH Protocol # and institution name.

Table 11.1 2014 Lugano Classification Response Criteria

Response	Site	CT-Based Response	PET-CT Based Response
Complete Response	Lymph nodes and extralymphatic sites	Complete radiologic response (all of the following) Target nodes/nodal masses must regress to ≤ 1.5 cm in longest diameter (LD). No extralymphatic sites of disease.	Complete metabolic response (even with a persistent mass) Score $\leq 3^*$ with or without a residual mass on 5-point scale [†] . It is recognized that in Waldeyer's ring or extranodal sites with high physiologic uptake or with activation within spleen or marrow (e.g., with chemotherapy or myeloid colony-stimulating factors), uptake may be greater than normal mediastinum and/or liver. In this circumstance, complete metabolic response may be inferred if uptake at sites of initial involvement is no greater than surrounding normal tissue

Response	Site	CT-Based Response	PET-CT Based Response
	Nonmeasured lesion	Absent	even if the tissue has high physiologic uptake.
	Organ enlargement	Regress to normal	Not applicable
	New lesions	None	None
	Bone marrow	Normal by morphology; if indeterminate, IHC negative	No evidence of FDG-avid disease in marrow
	Partial Response	Partial remission (all of the following)	Partial metabolic response
	Lymph nodes and extralymphatic sites	
≥ 50% decrease in SPD of up to 6 target measurable nodes and extranodal sites
 
When a lesion is too small to measure on CT, assign 5 mm X 5 mm as the default value
 
When no longer visible, 0 X 0 mm
 
For a node > 5 mm X 5 mm, but smaller than normal, use actual measurement for calculation
	
Score 4 or 5† with reduced uptake compared with baseline and residual mass(es) of any size
 
At interim, these findings suggest responding disease
 
At end of treatment, these findings indicate residual disease

	Nonmeasured lesion	Absent/normal, regressed, but no increase	Not applicable
	Organ enlargement	Spleen must have regressed by > 50% in length beyond normal	Not applicable
	New lesions	None	None
	Bone marrow	Not applicable	Residual uptake higher than uptake in normal marrow but reduced compared with baseline (diffuse uptake compatible with reactive changes from chemotherapy allowed). If there are persistent focal changes in the marrow in the context of a nodal response, consideration should be given to further evaluation with MRI or biopsy or an interval scan
No response or stable disease	Target nodes/nodal masses, extranodal lesions	Stable disease	No metabolic response
	Nonmeasured lesion	< 50% decrease from baseline in SPD of up to 6 dominant, measurable nodes and extranodal sites; no criteria for progressive disease are met	Score 4 or 5† with no significant change in FDG uptake from baseline at interim or end of treatment
	Nonmeasured lesion	No increase consistent with progression	Not applicable

Response	Site	CT-Based Response	PET-CT Based Response
Progressive disease	Organ enlargement	No increase consistent with progression	Not applicable
	New lesions	None	None
	Bone marrow	Not applicable	No change from baseline
Progressive disease requires at least 1 of the following		Progressive metabolic disease	
	Individual target nodes/nodal masses	PPD progression:	Score 4 or 5† with an increase in intensity of uptake from baseline and/or
	Extranodal lesions	An individual node/lesion must be abnormal with: Longest diameter (LDi) > 1.5 cm and Increase by \geq 50% from PPD nadir and An increase in LDi or shortest diameter (SDi) from nadir 0.5 cm for lesions \leq 2 cm 1.0 cm for lesions $>$ 2 cm In the setting of splenomegaly, the splenic length must increase by $>$ 50% of the extent of its prior increase beyond baseline (e.g., a 15-cm spleen must increase to $>$ 16 cm). If no prior splenomegaly, must increase by at least 2 cm from baseline New or recurrent splenomegaly	New FDG-avid foci consistent with lymphoma at interim OR end-of-treatment assessment
	Nonmeasured lesion	New or clear progression of preexisting nonmeasured lesions	None
	New lesions	Regrowth of previously resolved lesions A new node $>$ 1.5 cm in any axis A new extranodal site $>$ 1.0 cm in any axis; if $<$ 1.0 cm in any axis, its presence must be unequivocal and must be attributable to lymphoma Assessable disease of any size unequivocally attributable to lymphoma	New FDG-avid foci consistent with lymphoma rather than another etiology (eg, infection, inflammation). If uncertain regarding etiology of new lesions, biopsy or interval scan may be considered.
	Bone marrow	New or recurrent involvement	New or recurrent FDG-avid foci

Measured dominant lesions:

Up to six of the largest dominant nodes, nodal masses, and extranodal lesions selected to be clearly measurable in two diameters. Nodes should preferably be from disparate regions of the body and should include, where applicable, mediastinal and retroperitoneal areas.

Non-nodal lesions include those in solid organs (e.g., liver, spleen, kidneys, lungs), GI involvement, cutaneous lesions, or those noted on palpation.

Nonmeasured lesions:

Any disease not selected as measured, dominant disease and truly assessable disease should be considered not measured. These sites include any nodes, nodal masses, and extranodal sites not selected as dominant or measurable or that do not meet the requirements for measurability but are still considered abnormal, as well as truly assessable disease, which is any site of suspected disease that would be difficult to follow quantitatively with measurement, including pleural effusions, ascites, bone lesions, leptomeningeal disease, abdominal masses, and other lesions that cannot be confirmed and followed by imaging. In Waldeyer's ring or in extranodal sites (e.g., GI tract, liver, bone marrow), FDG uptake may be greater than in the mediastinum with complete metabolic response, but should be no higher than surrounding normal physiologic uptake (eg, with marrow activation as a result of chemotherapy or myeloid growth factors).

*A score of 3 in many patients indicates a good prognosis with standard treatment, especially if at the time of an interim scan. However, in trials involving PET where de-escalation is investigated, it may be preferable to consider a score of 3 as inadequate response (to avoid undertreatment).

†PET 5-point scale:

1, no uptake above background; 2, uptake \leq mediastinum; 3, uptake $>$ mediastinum but \leq liver; 4, uptake moderately $>$ liver; 5, uptake markedly higher than liver and/or new lesions; X, new areas of uptake unlikely to be related to lymphoma.

Abbreviations:

CT, computed tomography; FDG, fluorodeoxyglucose; IHC, immunohistochemistry; LDi, longest transverse diameter of a lesion; MRI, magnetic resonance imaging; PET, positron emission tomography; PPD, cross product of the LDi and perpendicular diameter; SDi, shortest axis perpendicular to the LDi; SPD, sum of the product of the perpendicular diameters for multiple lesions.

